Type 1 diabetes (T1D) is a complex metabolic disorder with pathophysiological disturbances beyond β -cell injury, including insulin resistance (IR) and mitochondrial dysfunction which are causally related to the development of diabetic kidney disease (DKD) and contributes to reduced life expectancy (1-6). Current treatments, such as control of hyperglycemia and hypertension, are beneficial, but only partially protect against DKD. Finding new, safe and effective therapies to halt DKD has proven to be challenging (7-14). A potential explanation is the narrow focus on the clinical manifestations of disease, e.g. hyperglycemia and hypertension. rather than identifying and targeting the initial underlying metabolic derangements driving DKD (15). The kidneys are highly metabolically active and are second only to the heart with respect to oxygen (O_2) consumption per tissue mass. The high O₂ demand is necessary to maintain adequate adenosine triphosphate (ATP) production for the Na⁺/K⁺-ATPase, as 95% of the ATP produced in the kidney is through aerobic metabolism (16, 17). Therefore, the principal determinant of renal ATP consumption is tubular reabsorption of filtered sodium (Na⁺). Experimental models suggest that T1D is associated with an environment that initially upregulates ATP consumption, due to: 1) increased Na⁺ reabsorption mediated by glucosuria, prolonged exogenous supraphysiological insulin exposure (18-23) and elevated Fig. 1 Type 1 Diabetes vasopressinergic and renin-angiotensin aldosterone system (RAAS) activity (24-27), and 2) increased *filtration* of Na⁺ due to elevated glomerular filtration L Ŧ Mitochondrial dysfunction rate (GFR, i.e. hyperfiltration) which is observed in up to 50% of youth with IR **↑**GFR **↑**ERPF T1D and predicts progressive DKD (28-30). Further, emerging animal data T suggest that in diabetes the kidneys are unable to sufficiently compensate for ↓ATP **↑**ATP the increased ATP consumption due to the effects of IR and mitochondrial generation consumption dysfunction on substrate utilization (impaired ATP generation, Fig 1) (19-22). Finally, the resultant ATP deficit is followed by increased perfusion or ↑Renal O₂ consumption effective renal plasma flow (ERPF) to deliver more O_2 to the kidney. However,

in the kidneys increased ERPF leads to increased GFR, and thus a higher Na⁺ load which further increases renal O₂ consumption.

Caffeine, a methylxanthine, is known to alter kidney function by several mechanisms including natriuresis, hemodynamics and renin-angiotensin-aldosterone system (31). In contrast, to other natriuretic agents, caffeine is thought to fully inhibit the local tubuloglomerular feedback (TGF) response to increased distal sodium delivery. This observation has broad-ranging implications as caffeine can reduce renal oxygen (O_2) consumption without impairing effective renal plasma flow (ERPF) and glomerular filtration rate (GFR). There are also data suggesting that chemicals in coffee besides caffeine may provide important cardio-renal protection (32). Yet, there are no data examining the impact of coffee-induced natriuresis on intrarenal hemodynamic function and renal energetics in youth-onset T1D. Our overarching hypothesis in the proposed pilot and feasibility trial is that coffee drinking improves renal oxygenation by reducing renal O₂ consumption without impairing GFR and ERPF. To address these hypotheses, we will measure GFR, ERPF, renal perfusion and oxygenation in response to 7 days of cold brew coffee (one Starbucks® Cold brew 325ml bottle daily [205mg caffeine]) in an open-label pilot and feasibility trial in 10 adolescents with T1D already enrolled in CASPER Study (#17-0820, PI: [name]).

SA1: To evaluate the impact of 7 days of coffee drinking on renal perfusion and oxygenation in adolescents with T1D.

- H1: Coffee drinking will improve renal oxygenation and perfusion in adolescents with T1D.
- SA2: To evaluate the impact of 7 days of coffee drinking on intrarenal hemodynamic function and tubular injury markers in youth with T1D.

H2.1: Coffee drinking will not significantly change GFR and ERPF in youth with T1D.

H2.2: Coffee drinking will decrease concentrations of tubular injury markers in youth with T1D.

II. Background and Significance: Over 1.25 million Americans have T1D, increasing risk for early death from cardiovascular disease (CVD) (33, 34). Despite advances in glycemic and blood pressure control, a child diagnosed with T1D is expected to live up to 17 years less than non-diabetic peers (1-4). The strongest risk factor for CVD and mortality in T1D is DKD (5, 6). Current treatments, such as control of hyperglycemia and hypertension, are beneficial, but only partially protect against DKD (7-14). This limited progress may relate to a narrow focus on clinical manifestations of disease, rather than on the initial metabolic derangements underlying the initiation of DKD (15). Renal hypoxia, stemming from a potential metabolic mismatch between increased renal energy expenditure and impaired substrate utilization, is increasingly proposed as a unifying early pathway in the development of DKD (21, 35, 36). T1D is impacted by several mechanisms which *increase renal ATP consumption* and *decrease ATP generation*.

Caffeine is known to modify renal function by several mechanisms including natriuresis, hemodynamics and renin-angiotensin-aldosterone system. Caffeine is also thought to inhibit the expression of the Na⁺/K⁺ ATP pump and isoform 3 of the Na⁺/H⁺ exchange; both are key proteins in the mechanism of active/passive tubular reabsorption (31). In contrast, to other natriuretic agents, caffeine is theorized to fully inhibit the local TGF response to increased distal Na⁺ delivery. This observation has broad-ranging implications as caffeine can reduce renal O_2 consumption (by inhibiting Na⁺ reabsorption which accounts for the majority of renal O_2 consumption) without impairing ERPF and GFR. Such mechanisms can provide protection from acute and chronic tubular and glomerular injuries. There are also important non-renal mechanisms hypothesized to explain the potential protective effect of coffee drinking on mortality including reduced inflammation, improved insulin sensitivity, and endothelial function (37-39).

*Rigor of the prior research:* To our knowledge, there are no studies examining the impact of coffee or caffeineinduced natriuresis on intrarenal hemodynamic function and renal energetics in youth with T1D. Our preliminary data suggest that coffee intake protects against acute kidney injury (see below), and recent findings from the UK Biobank reports an inverse relationship between caffeinated and non-caffeinated coffee drinking and mortality (32). Therefore, the UK Biobank data strongly support the importance of noncaffeine constituents in the coffee-mortality association (32). Consistent with these data, recently published data also demonstrate that daily coffee intake is associated with decreased risk of development of chronic kidney disease {Jhee, 2018 #15851}. Accordingly, it is important to evaluate the effect of coffee rather than simply caffeine on intrarenal hemodynamic function and energetics (oxygenation). In addition, brews are thought to

contain a higher number of bioactive compounds including polyphenols than instant coffee (40). Further, cold brews are proposed to retain the bioactive compounds better through their slower brewing process compared to hot brews (41).

Our overall hypothesis in this pilot and feasibility trial is that cold brew coffee drinking for 7 days improves renal oxygenation by reducing renal O_2 consumption, without impairing GFR and ERPF (**Fig 2**).

[figure not shown]

Fig 2 Proposed Mechanism of Coffee Drinking on Renal Function

Impact: Clinical trials in DKD have yielded disappointing results for the past two decades. This trend may be explained in part by the lack of understanding around what initiates early DKD, and by failing to intervene at the initial stage of the disease when benefit may be maximally achieved. This proposal seeks to investigate the effect of coffee on intrarenal hemodynamics, renal perfusion and oxygenation in youth-onset T1D. Given the global diabetes and obesity epidemic, the ability to potentially reduce renal O₂ consumption and increase renal oxygenation without the TGF-mediated reduction in ERPF and GFR, provides a strategic approach to reduce the huge burden of DKD, a major cause of morbidity and premature mortality. This pilot and feasibility study will provide preliminary data and direct a larger clinical trial.

III. Preliminary Studies/Progress Report:

Hyperfiltration is common in youth and adults with T1D, and predicts rapid GFR decline and impaired GFR: We demonstrated that the prevalence of hyperfiltration in youth and young adults with T1D can exceed 50% when GFR is measured by inulin clearance (28), and between 13-31 % when GFR is estimated by serum creatinine and serum cystatin C (42, 43). The discrepancy in prevalence is likely attributed to the inaccuracy of estimated GFR in the normal to elevated GFR range (44), hence we propose to measure GFR in this study. In adults with T1D (n=646) in CACTI, we also demonstrated that hyperfiltration predicted greater odds of rapid GFR decline over 6-years (OR: 5.00, p<0.0001), when adjusting for traditional risk factors including HbA1c, systolic blood pressure (SBP), LDL-C, sex, duration and albumin-to-creatinine ratio (ACR) (44). Furthermore, over 12-year follow-up in CACTI, adults with T1D who experienced rapid GFR decline (annual GFR loss > 3mL/min/1.73m²) were more likely to demonstrate hyperfiltration at baseline (OR: 32.9, p<0.0001) and impaired GFR at 12-year follow-up (OR: 11.6, p=0.0003) (unpublished data). In a parallel analysis we conducted in CACTI and the Pittsburgh Epidemiology of Diabetes Complications Study (EDC), elevated GFR at baseline was associated with a greater odds of rapid GFR decline over 6 and 8-years respectively (CACTI: OR 2.62, p<0.0001, EDC: OR 2.16, p=0.0003) (45).

BOLD and ASL MRI demonstrate decreased renal oxygenation in chronic kidney disease (CKD): Our collaborator, [name] demonstrated that adults with CKD have lower renal cortical oxygenation compared to controls (18.0±1.62 *vs.* 20.6±3.4 s⁻¹, p<0.0001) by BOLD MRI (46). Furthermore, renal perfusion measured by ASL MRI correlated strongly with eGFR (r=0.67, p<0.0001) (47).

Coffee consumption is associated with lower risk of acute kidney injury (AKI): Unpublished data from

Atherosclerosis Risk in Communities Study (ARIC, [name]) found an inverse relationship between any coffee consumption and AKI risk (**Table 1**). Furthermore, there was a stepwise relationship between number of cups of coffee per day and AKI risk (≥ 3 cups / day: 0.72 [0.61, 0.86], 2-3 cups/day: 0.75 [0.63, 0.90], 1-2 cups/day: 0.86 [0.75, 0.99], <1 cup/day: 0.83 [0.71, 0.96] compared to never: 1.00 [reference group]).

| Table 1 | | |
|---------------------------------|--------------------|--------------------------|
| Acute Kidney Injury | Never (n=2,746) | Any Coffee (n=11,461) |

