Potential scientific problems: In any clinical study, unforeseen human factors provide challenges. We have experience with hyperglycemic clamps, iohexol and PAH clearance studies and MRI methods in youth with T1D and have already obtained preliminary data. We anticipate an increase in renal oxygenation due to decreased renal oxygen consumption with preserved GFR and ERPF in response to coffee therapy. In addition, we expect decreased plasma concentration of tubular injury markers in response to coffee therapy. Clearance of PAH is the gold standard method to measure ERPF, and GFR by iohexol clearance is more accurate and precise than eGFR. Importantly, iohexol and PAH clearances do not interfere with the assessment of insulin sensitivity during a hyperglycemic clamp. Mild hyperglycemia (~ 190mg/dl) during the GFR measurements and a salt replete and protein controlled diet are critical strengths as severe hyperglycemia acutely increases GFR, and salt and protein intake influence intrarenal hemodynamics (97). Furthermore, mild hyperglycemia allows us to quantify intrarenal hemodynamic function in a glycemic milieu similar to their native pathophysiology. In contrast, a hyperinsulinemic-euglycemic clamp would render the participants completely normoglycemic, which does not reflect their usual glycemic environment, and expose them to high concentrations of insulin which may interfere with the assessment of their intrarenal hemodynamic function. Based on our preliminary work, we expect the 2 renal sequences (BOLD and ASL) to be completed within 60 min. In our other studies we have had adolescents with T1D, T2D and without diabetes undergo similar MRI procedures lasting 120 min, indicating that recruiting and tolerability in youth for such procedures are feasible. Our research MRI is equipped with in-MRI movie-viewing with noise-cancelling headphones and thus is very tolerable to youth. The participant will be monitored by heart rate, blood pressure, and oxygen saturation measurements, and will be able to communicate with the MRI technician and investigator immediately outside of the scanner. As BOLD is potentially influenced by O₂ delivery (ERPF) and O₂ consumption (tubular Na transport accounts a majority of renal O₂ consumption (103)) we will control for ERPF and fractional excretion of sodium (FeNa). We will perform the MRI after the clamp to remove the effects of acute variations in glycemia on RPF. Participants on medications that might alter O₂ delivery and/or consumption, e.g. angiotensin-converting enzyme inhibitors (ACE-I), angiotensin receptor blockers (ARBs) and diuretics will be excluded.

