Evidence of Benefit to Society: The importance of the knowledge gained from this protocol is high, since DKD is very prevalent in T1D and increases the risk of death from CVD and shortens lifespan. In fact, T2D in youth is increasing in prevalence in parallel with the obesity epidemic. In the United States, almost half of patients with renal failure have DKD. Despite the high prevalence and gravity of DKD in youth onset T1D, widely effective therapeutic options are lacking. Diabetes mellitus is the third most prevalent severe chronic disease of childhood. DKD remains a leading cause of morbidity and mortality, and a major risk factor for CVD in diabetes. Although data to guide care of DKD in adults with diabetes are limited, even less data exist regarding the antecedents of DKD in youth with diabetes. Yet, these antecedents of adult DKD are present in childhood, data to inform clinicians as to treatment in this high-risk population are of great public health importance. In our novel and innovative proposal, we postulate that coffee will decrease renal oxygen consumption, thereby improving renal oxygenation without impairing GFR and ERPF. Knowledge gained from this proposal will provide new information about the effects of coffee on renal energetics and intrarenal hemodynamic function in T1D. The investigative team is also unique in being one the few groups skilled in performing both gold standard renal physiology studies and advanced MRI evaluation in youth with T1D.

G. Data Analysis Plan (formulated with biostatistician [name] PhD):

Aim 1-2 Power calculations, statistical analysis, rigor and reproducibility: For this initial pilot and feasibility trial, we plan to recruit 10 youth. Power calculations are based on paired *t*-tests. A sample size of 10 provides 80% power to detect a mean paired difference of 0.44 SD for renal oxygenation and tubular injury markers. The following variables will be considered for inclusion in models as confounders: response: age, sex, ethnicity, T2D duration, HbA1c, BP, LDL-C and FeNa. We will use paired *t*-test and McNemar's test in addition to multivariable linear models of the change in each outcome, adjusted for potential confounders. This is a pilot and feasibility study and the data should be considered hypothesis generating. We acknowledge that we may be underpowered for multivariable modeling, and our primary analyses will be unadjusted.

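### H2.1 predicts no significant change in GFR and ERPF, but the plan offers only difference tests in 10 participants, with no margin, interval criterion or power for these outcomes

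*Combined protocol and SAP*

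**What the plan says.** H2.1, under SA2 in the opening aims, reads: "Coffee drinking will not significantly change GFR and ERPF in youth with T1D". The same idea runs through the rest of the protocol:

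- Section II (Background and Significance) gives the overall hypothesis: coffee improves oxygenation by lowering renal oxygen "consumption, without impairing GFR and ERPF".
- Section II also explains why this matters for caffeine: "In contrast, to other natriuretic agents, caffeine is theorized to fully inhibit the local TGF response".
- Section E (Potential Scientific Problems and Feasibility): "We anticipate an increase in renal oxygenation due to decreased renal oxygen consumption with preserved GFR and ERPF".
- Section F (Potential Benefits): "we postulate that coffee will decrease renal oxygen consumption, thereby improving renal oxygenation without impairing GFR and ERPF".

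GFR by iohexol clearance and ERPF by PAH clearance are listed as Aim 2 outcomes in section A (Outcome Measures).

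The analysis is in section G. It names the paired t-test, McNemar's test and "multivariable linear models of the change in each outcome, adjusted for potential confounders", with the unadjusted analysis as primary. Its power statement is: "A sample size of 10 provides 80% power to detect a mean paired difference of 0.44 SD for renal oxygenation and tubular injury markers". GFR and ERPF are not in that sentence. Section G adds that "the data should be considered hypothesis generating". It concedes possible low power, but only for the multivariable models.

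**The concern.** H1 and H2.2 predict a change, so low power works against them. H2.1 predicts the absence of a significant change, so low power works in its favour: the less precise the study, the more likely the predicted result. The general caveat about a hypothesis-generating pilot does not correct for this, because it does not say how a null result for GFR or ERPF is to be read.

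A large fall would probably be detected and would contradict H2.1. A moderate fall would often be non-significant and, as H2.1 is worded, would agree with it. This is the property that the opening summary and section II use to set caffeine apart from other natriuretic agents, and section II says the pilot will direct a larger trial. A message that filtration and plasma flow were preserved, resting only on non-significance in 10 people, could pass into that design.

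**Working it through.** **Inputs.** From section G: n = 10, paired t-test, unadjusted analysis primary. Not stated anywhere, so assumed here: two-sided alpha 0.05 and 10 complete pairs. No SD of change is given for GFR or ERPF, so effects are expressed first in SDs of the paired change (δ).

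**The plan's own power figure.** Section G gives 0.44 SD at 80% power, for other outcomes. Under the plain reading (SD of the paired differences), n = 10 with two-sided 0.05 needs 0.996 SD for 80% power, and power at 0.44 SD is about 24%. The figure is recovered only if SD means the between-subject SD and the pre/post correlation is about 0.90, which the plan does not state. That is a separate matter. Here it means only that 0.44 SD cannot be borrowed for GFR or ERPF.

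**Chance of a non-significant result.** The test statistic follows a noncentral t with df = 9 and noncentrality δ√10. The critical value is t(0.975, 9) = 2.262. The chance sought is P(|T| < 2.262).

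| True change δ (SD of change) | δ√10 | P(non-significant) |
|---|---|---|
| 0.5 | 1.58 | 0.707 |
| 0.75 | 2.37 | 0.438 |
| 1.0 | 3.16 | 0.197 |
| 1.5 | 4.74 | 0.013 |
| 2.0 | 6.32 | 0.0002 |

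**Width of the interval.** The 95% half-width is 2.262/√10 = 0.715 of the observed SD of change. At exactly p = 0.05 the near limit is zero and the far limit is 2 × 0.715 = 1.43 SD. That is the extreme case of a result just short of significance.

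**In GFR units.** The SDs and the 10-unit fall below are illustrations, not figures from the documents (ml/min/1.73m²).

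| Assumed SD of change | δ for a 10-unit fall | P(non-significant) | 95% half-width |
|---|---|---|---|
| 5 | 2.0 | 0.0002 | 3.6 |
| 10 | 1.0 | 0.197 | 7.2 |
| 15 | 0.67 | 0.531 | 10.7 |
| 20 | 0.5 | 0.707 | 14.3 |
| 30 | 0.33 | 0.843 | 21.5 |

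**If a margin were used.** With an observed change of exactly zero, the margin must exceed 0.715 SD for a 95% interval to lie inside it, or 0.58 SD for the 90% interval usual in a 5% equivalence test. With a true change of zero, 80% power at n = 10 needs a margin of about 1.00 SD with the 90% interval and 1.15 SD with the 95% interval.

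**The case against.** The strongest reply is that the plan never says p > 0.05 means preserved. H2.1 can be read as a scientific expectation. The protocol uses similar words loosely when it explains why DXA is not repeated, where no test is meant. The parent aim, SA2, is already about evaluating an effect, and paired t-tests and linear models yield a mean change and an interval as a matter of course. The study is labelled a pilot, and sections E and F speak of what is anticipated and postulated. No SD of change is available, so the chance of missing a 10-unit fall runs from about 0% to 84% depending on the assumption. The clamp and the diet instructions may keep the SD small. Finally, with one open-label arm measured before and after, no interval or margin could by itself attribute stable function to coffee.

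Much of this stands, and it keeps the severity low. It does not remove the point. Even read as an expectation, H2.1 is phrased in terms of significance and paired with difference tests, and the plan gives no other way to judge it. That intervals could be produced is not a commitment to report them or to use them for H2.1. Nothing in the documents shows that the SD of change is small. The limits of the design are a further reason not to read preservation into a null test.

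**Conclusion.** The concern holds. H2.1 is worded as a non-significant result, and the plan supplies no margin, interval criterion or power for GFR or ERPF. With 10 complete pairs and two-sided alpha 0.05 (both assumed), a true change of 0.5 to 1.0 SD of the paired change would be non-significant between 71% and 20% of the time and would count as agreement with the hypothesis. Changes of 1.5 SD or more would nearly always be detected. What this means in ml/min rests on an SD that the documents do not give. If it is near 5 ml/min/1.73m², the concern largely disappears for a 10-unit GFR fall; at 15 or above, such a fall is missed more often than not. The consequence is limited because the trial is an exploratory pilot, but the correction should be made because it changes what can be concluded about GFR and ERPF.

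**What to change.** 1. Reword H2.1 as an estimation aim: to estimate the change in GFR and in ERPF after 7 days of coffee.
2. In section G, state that the mean paired change in each will be reported with a two-sided 95% confidence interval, and that a non-significant result with 10 participants is not by itself evidence of preserved function.
3. Optionally, if a claim of preserved or unimpaired function is wanted, the sponsor should prespecify and justify a margin for GFR and for ERPF, and state the SD of change on which it relies. This would be hard to meet with 10 participants.

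The first two changes cost one reworded hypothesis, one added sentence and two intervals from data already collected. No new participants or procedures are needed. The one drawback is that preservation will be claimed less often. A margin costs more, because it needs a clinical justification and an SD of change that the documents do not contain.
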